Aim 3: To conduct preliminary analyses exploring whether emerging adults who receive the intervention demonstrate improvement in key symptom domains. Specifically, 40 youth will be randomized to either the integrated treatment or standard care. Primary outcomes will include substance abuse and PTSD. Secondary outcomes will include criminal justice involvement, adaptive functioning, and other mental health symptoms.

The results of the study will have a **significant impact on public health** by informing treatments for co-occurring SUD/PTSD among justice-involved transition age youth, a group at the highest risk for these problems. Demonstrating the efficacy of an integrated treatment approach will provide a valuable clinical tool for community-based therapists to employ in the context of existing evidence-based treatments. Further, should compelling indications of efficacy be found and safety and acceptability be established, these aims will position the research to advance to an appropriately powered randomized controlled trial.

A. SIGNIFICANCE

Prevalence and consequences of substance use problems among emerging adults. Transition age youth (i.e., emerging adults, ages 18-25) represent the age group with the **highest rates of initiation of substance use, increases in substance use, and progression of substance use into substance use disorders** (Chassin, Flora, & King, 2004; Delucchi, Matzger, & Weisner, 2008; SAMHSA, 2009). Substance use plays a significant role in many serious problems during this developmental period, including suicide (SAMHSA, 2010), automobile accidents (Hingson, Heeren, Winter, & Wechsler, 2005), and other lethal events. Emerging adults with SUDs also have increased rates of risky sexual behavior, increasing their chances of contracting HIV and other STDs (King, Nguyen, Kosterman, Bailey, & Hawkins, 2012). Further, SUDs significantly impede successful negotiation of important developmental tasks of this transitional age, leading to increased rates of unemployment and job instability and decreased college attendance (Bray et al., 2000; Mangione et al., 1999). Finally, emerging adults with SUDs represent a greatly underserved population, with a high likelihood of “slipping through the cracks” as they transition from child to adult substance use service providers ([name], Green, & Hoffman, 2009). **Thus, this group has a very high potential to present significant short- and long-term costs for individuals, families, and society.**

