Random Assignment occurs after the BL evaluation. A computerized urn randomization procedure (Stout et al., 1994) will balance patients on gender and submission of a positive sample for any illicit drug (i.e., cocaine, amphetamine, methamphetamine, opiate, benzodiazepine, or marijuana) at baseline, because positive samples at treatment initiation are related to poor outcomes (Preston et al., 1998; Silverman et al., 1998; Stitzer et al., 2007). Prior to randomizing participants, up to 10 pilot participants will complete a pilot study consent form and study procedures described for Group B below, through month 3 follow-up, for the purpose of monitoring staff on study procedures prior to the randomized trial.

Group A (Standard care [SC]; n=20) patients will receive SC at the substance use clinic where they are seeking treatment. This treatment approach typically consists of group therapy sessions, including daily planning, 12-Step treatment, relapse prevention, coping and life skills training, and AIDS education. Groups are led by recovering individuals, nurses, and masters level counselors. Very few individual sessions are provided at these clinics, and then only in cases of emergencies (e.g., suicidality). These clinics rarely conduct breathalyzers or urine testing for illicit drug use. Any such testing will occur as it normally would, and study procedures will not

impact standard care in any way. If the participant is not already enrolled in SC at a substance use clinic, they will be provided with referrals to clinics convenient to their home.

Study urine samples will be collected twice weekly. Patients will receive a \$5 payment (check or gift cards) for each of 20 urine/breath sample submissions during weeks 1-10. In addition, they will be asked to complete the NSSEP-SS and the CES-D to assess PTSD symptoms and depression weekly. If patients cease attending groups, they will still be encouraged to attend these brief meetings for sample monitoring. To maintain consistency with standard care in these clinics, results from toxicology screens will not be discussed with providers.

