Group B (SC + PE/CM Treatment; n=20) patients will receive the same SC groups as Group A. If they are currently enrolled in substance use treatment, they will continue with that treatment. If not, they will be provided with referrals for substance use treatment in the community. In addition, they will participate in an integrated Contingency Management (CM) and Prolonged Exposure (PE) treatment protocol described subsequently. Either the PI ([name]) or [name], will serve as the study therapist for participants randomized to group B. For cases where [name] serves as the therapist, [name] will provide clinical supervision of study cases.

As in Group A, participants will undergo testing twice weekly with a breathalyzer and urine drug screen. In addition, during the first meeting of the week, participants will engage in both CM and PE components of treatment (described below). During the second meeting of the week, participants will engage in CM and a brief check-in on the components of PE that the participant is working on for homework that week but no new PE-related components will be introduced.

Contingency Management Component. Participants in Group B will participate in CM to target abstinence from substance use. In prize CM protocols, participants earn opportunities to draw cards from a prize bowl. The cards differ in prize value, ranging from \$0 to \$100 in value, and participants can earn increasing numbers of draws with consecutive performance. The variable reinforcement amount feature of prize CM distinguishes it from other reinforcement systems such as voucher CM. Participants will be allowed to draw from the prize bowl if their urine drug screen is negative for opiates, methadone, cocaine, amphetamines, methamphetamines, and marijuana (see additional information about marijuana use below) and their breath screen is negative for alcohol.

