Feasibility measures relevant to recruitment and dropout proportions will be examined with 95% confidence intervals used to estimate the proportion of emerging adults who agree to participate out of the number deemed eligible and to compare those who complete versus do not complete the intervention. Feasibility will be evaluated by examining therapist adherence using ratings of taped sessions as well as emerging adults' responses to qualitative interviews. Measures of safety will include repeat trauma exposure, suicidal ideation, and risky substance use behaviors. Patterns of safety indicators will be examined using frequency distributions and descriptive statistics. In addition, rates of these indicators will be compared across Group A and Group B to determine if there is any increased risk posed by the active treatment compared to treatment as usual. These data will be used to make any necessary protocol changes.

Aim 3: To conduct a preliminary analysis of the efficacy of the integrated protocol in improving symptoms among emerging adults.

Groups will be compared with respect to the primary outcome variables (substance use, PTSD symptoms) and secondary variables (delinquent behaviors, depression, adaptive functioning, HIV risk behaviors). An important issue preceding analyses is to identify baseline differences between groups despite random assignment. Differences between groups that may be related to outcome will be used as covariates or fixed factors, as appropriate. We will conduct intent-to-treat analyses, with all randomized patients and apply random regression models, also known as hierarchical linear models (HLM), to determine if patients improve differentially between groups over time (Raudenbush & Bryk, 2002). HLM is specifically designed for repeated measures designs with missing data, allowing for intra-subject serial correlation and unequal variance and covariance structures over time by incorporating available trend data for each individual with information on the group from which the subject is drawn. Maximum likelihood estimation enables analyses to be performed for the full trial without having to drop subjects with incomplete data, and both continuous and dichotomous variables can be analyzed. If data cannot be normalized, group by time effects will

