Effects of treatment on PTSD symptoms will be examined primarily using the weekly scores on the NSESP-SS. This is a continuous measure, with missing data likely. If no systematic differences in missing data are noted (the case in our prior studies), hierarchical linear models (HLM; Gibbons et al., 1993) using MIXREG (Hedeker, 1993) will analyze differences between groups over time. These analyses have advantages over repeated measures ANOVA as they estimate missing data via model parameter estimates and use real time, rather than scheduled time, of assessments. The model will include factors for group, time, and the interaction of group by time.

Secondary outcomes include delinquent behaviors (SRD), HIV risk behaviors (HRSB), adaptive functioning (SAS-SR), and depression (CES-D). Using the same HLM modeling described above, we will examine the impact of group, time, and group x time on each of these secondary outcomes to determine if the PE/CM treatment produces better outcomes than usual services.

Contingency Plan: If the intervention is not found to be feasible and/or produce symptom reduction, the candidate will work closely with mentors during Yr 5 to evaluate where positive outcomes are lacking and to refine the intervention using both quantitative and qualitative approaches. Assessment results will be evaluated to determine whether the intervention is equally effective across all areas targeted in treatment. If the intervention is found to be less effective in a specific area, modifications will be made to enhance the intervention in that area. Data will be examined to determine whether specific factors explain differential effects among participants. Input from participants will also be a critical source of information for improving the intervention.

PROTECTION OF HUMAN SUBJECTS

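### For the continuous outcomes analysed by HLM, the plan names maximum likelihood with no small-sample correction at N = 40; REML with adjusted degrees of freedom is a cheap improvement

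*Combined protocol and SAP*

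**What the plan says.** The Specific Aims state that "40 youth will be randomized to either the integrated treatment or standard care". The arm descriptions give 20 per group: "Group A (Standard care [SC]; n=20" and "Group B (SC + PE/CM Treatment; n=20".

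Under Data Analysis Strategy, Aim 3, group-by-time effects are to be assessed by HLM in all randomized patients. The only estimator named is in this sentence: "Maximum likelihood estimation enables analyses to be performed for the full trial without having to drop subjects with incomplete data". The same sentence covers continuous and dichotomous variables. A later paragraph says that, for the weekly NSESP-SS, HLM "using MIXREG (Hedeker, 1993) will analyze differences between groups over time", with group, time and their interaction as factors. The same modelling is carried over to delinquency, HIV risk, adaptive functioning and depression. Baseline differences that may relate to outcome are to be added as covariates or fixed factors.

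Three things are not stated for these models: the reference distribution or degrees of freedom, the random-effects or covariance structure, and a significance level. The one interval level given is in Aim 2: "95% confidence intervals used to estimate the proportion of emerging adults who agree to participate".

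Two groups of outcomes lie outside this point. LDA is planned as a linear regression with a nonparametric fallback, and the proportion of negative samples by similar analyses. Outcomes that cannot be normalized are recoded as improved or not, and REML as discussed here does not apply to them.

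**The concern.** ML estimates the variance components as if the fixed effects were known. With 40 participants that makes the standard error of the group-by-time effect a little too small. If the estimate is then referred to a normal distribution, the uncertainty in the variance estimate is ignored as well. Both errors act in the same direction: intervals are too short and the test rejects too often.

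The reason the plan gives for ML is that incomplete cases stay in the analysis. REML is also likelihood-based and keeps the same cases, so that reason does not favour ML.

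The models affected carry one of the two primary outcomes and the secondary outcomes that stay continuous. The results are meant to inform further work; the Specific Aims say that, given compelling indications of efficacy together with safety and acceptability, "these aims will position the research to advance to an appropriately powered randomized controlled trial".

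**Working it through.** **No figure to reproduce.** The plan gives no alpha, power, effect size or variance for Aim 3.

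**Inputs**
- From the documents: N = 40, 20 per arm; group, time and group × time as fixed effects; weekly scores over about 10 weeks.
- Assumed: two-sided 5% level (z = 1.960); random intercept and slope per participant; standardized slope differences of 0.5 to 1.0 for the cost calculation.

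**1. Balanced case, exact.** With complete data the group × time test reduces to a two-sample comparison of participants' slopes. ML divides the slope variance by N and REML by N − 2.
- SE ratio, ML to REML = √(38/40) = 0.975, so the ML standard error is 2.5% too small.
- ML with z rejects when |t(38)| > 1.960 × 0.9747 = 1.910. Type I error = 2·P(t(38) > 1.910) = **6.37%**.
- With 36 analysed: threshold 1.960 × √(34/36) = 1.905, giving 6.53%. With 30: 1.960 × √(28/30) = 1.894, giving 6.87%.

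**2. Which part comes from what (N = 40)**

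| Estimator and reference | Rejects when abs. t(38) exceeds | Type I error |
|---|---|---|
| ML, z | 1.910 | 6.37% |
| REML, z | 1.960 | 5.74% |
| ML, t(38) | 2.024 × 0.9747 = 1.973 | 5.58% |
| REML, t(38) | 2.024 | 5.00% |

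**3. Covariates.** If k between-subject covariates take degrees of freedom from the tested contrast (that is, they also enter the slope comparison), ML with z gives 2·P(t(38−k) > 1.960·√((38−k)/40)).
- k = 2: threshold 1.859 on 36 df, 7.1%.
- k = 4: threshold 1.807 on 34 df, 8.0%.

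**4. Simulation under the null.** There were 2,000 trials per row with 20 per arm. Assumed SDs: intercept 0.7, residual 0.5, slope 0.06 per week (0.03 for three visits). Monte Carlo SE is about √(0.06 × 0.94/2000) = 0.5 points.

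| Schedule, dropout | Fitted random effects | ML, z | REML, Satterthwaite |
|---|---|---|---|
| 11 weekly, none | intercept + slope | 7.0% | 5.3% |
| 11 weekly, 30% | intercept + slope | 7.0% | 5.3% |
| 11 weekly, 50% | intercept + slope | 7.3% | 5.0% |
| 3 visits, 10% | intercept + slope | 7.2% | 5.5% |
| 11 weekly, none | intercept only, slopes truly vary | 19.2% | 18.9% |

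The dropout rates are assumptions. The plan expects more than 90% follow-up through month 6 but says that missing weekly scores are likely.

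**5. Cost of the change (N = 40)**
- Ratio of interval widths = 2.024/(1.960 × 0.9747) = 1.060, so 95% intervals are 6.0% wider.
- Power from the noncentral t with 38 df and noncentrality d·√(40/4):

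| d | ML, z | REML, t(38) |
|---|---|---|
| 0.5 | 37.9% | 33.8% |
| 0.8 | 73.2% | 69.3% |
| 1.0 | 89.2% | 86.9% |

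**The case against.** The strongest reply is that the quoted sentence is about missing data. It does not set full ML against REML, and nothing in the plan says that the tests use z. MIXREG's settings are not given either. A reader might infer that the plan has committed to ML with z tests, but the documents do not support that. What stands is narrower: ML is the only estimator named, and no small-sample correction accompanies it. The z reference is an assumption, although with a t reference ML still gives 5.6%.

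A reader might also extend the point to all continuous outcomes. That fails, because the LDA regression already uses residual degrees of freedom in its usual t test.

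It can further be said that the inflation hardly matters in a pilot. The balanced-case effect estimate is the same under both estimators, no confirmatory threshold is set, and the Overview of Design ties the next application to evidence of feasibility. This is a fair argument for low severity. It is not a reason to keep the less accurate method when the alternative needs no extra participants or data.

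**Conclusion.** The point holds as a cheap improvement of low severity, limited to the NSESP-SS and the other HLM-analysed outcomes that remain continuous. With ML and a z reference at an assumed two-sided 5% level, type I error is 6.4% in the balanced case, 7.0% to 7.3% in the simulations with a correct covariance model, and 7.1% to 8.0% in the balanced formula with two to four covariates of the kind described. REML with a suitable t reference gives 5.0% exactly in the balanced case and 5.0% to 5.5% in those simulations.

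It is tempting to conclude that switching to REML restores the nominal rate at no cost. Neither half is supported. Restoration depends on an adequate random-effects structure, which the plan leaves open. With a random intercept only and slopes that truly vary, both methods reject about 19% of the time, a much larger error than the choice between ML and REML. The change also costs some interval width and nominal power, which is the price of correct error control.

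**What to change.** In Data Analysis Strategy, Aim 3, amend the paragraph that introduces HLM and the paragraph on the NSESP-SS along these lines:

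*HLMs for continuous outcomes will be fitted by REML with a random intercept and random slope for each participant (or another adequate covariance structure named in advance). Tests and 95% confidence intervals will use Kenward-Roger or Satterthwaite degrees of freedom. ML will be used only for likelihood-ratio comparison of fixed-effect structures.*

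State the significance level and sidedness in the same place. If MIXREG does not support these options, name software that does. Leave the LDA and proportion-of-negative-samples regressions and the dichotomous HLMs as they are.

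The cost is a few sentences, possibly different software, and the wider intervals and lower nominal power shown above. No additional participants, visits or data are needed.

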The Trauma Assessment for Adults (TAA; Gray, Elhai, Owen, & Monroe, 2009) will be used to screen for exposure to traumatic events, as the diagnosis of PTSD or subthreshold PTSD is contingent upon the experience of a qualifying traumatic event. In addition, the TAA assesses current involvement in violent relationships and will be used to assess the exclusion criteria "currently in a domestic violence relationship."

The National Stressful Events Survey PTSD Short Scale (NSESP-SS) (Miller et al., 2013), a validated self-report measure of DSM-V PTSD symptoms, will be used to screen for PTSD. THE NSESP-SS is a 20-item measure including subscales for intrusion, avoidance, negative cognitive/mood alterations, and hyperarousal/reactivity. The reference period will be "since the crime event occurred" at the screening/BL assessment and "past month" for each subsequent assessment. It is likely that emerging adults with both clinical and sub-clinical levels of PTSD will benefit from this treatment; therefore, emerging adults will meet study criteria if they: (a) report an index trauma; (b) meet criteria for 2 of the 4 DSM-V PTSD symptom cluster and (d) have significant functional impairment (i.e., the recommendation for determining subthreshold PTSD using DSM-V criteria; McLaughlin et al., 2015). This instrument will be used at each of the assessments as well as once per week during the participant's scheduled sessions.

The Addiction Severity Index (ASI) (McLellan et al., 1988) is a structured interview that assesses demographic information as well as areas affected by substance use disorders: alcohol use, drug use, medical status, legal status, psychiatric, employment, gambling, cigarette smoking, and social functioning. Adequate interrater and test-retest reliability, and concurrent and discriminant validity, have been established (McLellan et al., 1985; Zanis et al., 1994). An abbreviated version will be administered at follow-up.

Timeline Follow-back (TLFB; Sobell et al., 1980) uses calendar prompts to elicit specific information about the frequency and intensity of substance use over time intervals with good test-retest reliability and validity (Sobell & Sobell, 1992). It will assess days and quantity of alcohol use and days of cocaine, opioid, benzodiazepine, marijuana or other drug use 3 months before treatment, every session throughout treatment, and since the last interview at follow-up.

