The Psychiatric Diagnostic Screening Questionnaire (PDSQ) (Zimmerman & Shereen, 2003) is a brief, psychometrically strong self-report scale that screens for the most common Axis I DSM-IV disorders encountered in outpatient settings. For the current study, modules for the following disorders will be used: 1) obsessive compulsive disorder; 2) panic disorder; 3) psychotic symptoms; 4) agoraphobia; 5) social phobia; 6) generalized anxiety disorder; 7) physical health problems; and 8) hypochondria.

The HIV Risk Behavior Scale (HRBS; Darke et al., 1991) assesses injection and sexual risk behaviors over time; it has adequate reliability and validity (Barry et al., 2008; Petry, 2001) and provides continuous summary scores. The HRBS will assess lifetime and past 3 months at baseline and the past 3 months at all other time points.

The Quality of Life Inventory (QOL; Frisch, et al., 1992) assesses satisfaction in 17 life areas (work, health, recreation, goals, etc). It has test-retest coefficients of .80-.91 and correlates with other measures of well-being (Frisch, et al., 1992); scores change in response to CM (Petry et al., 2007b).

The COPE Inventory (COPE; Carver, Scheier, & Weintraub, 1989) is a well validated measure of a broad range of coping responses that individuals use in response to stress. Five scales measure aspects of emotion-focused coping (e.g., seeking of emotional social support, positive reinterpretation, acceptance, denial, turning to religion); and three scales that measure less adaptive coping strategies (e.g., focusing on and venting of emotions, behavioral disengagement, mental disengagement).

The Center for Epidemiological Studies-Depressed Mood scale (CES-D; Radloff, 1977; Thomas et al., 2001) is a widely used, reliable and valid index for assessing depressive symptoms. This instrument will be used at each of the assessments as well as once per week during the participant's scheduled sessions.

The Self-Reported Offending Scale (SRO; Huizinga, 1991) was adapted from the Self-Reported Delinquency Scale (Elliott, Ageton, Huizinga, Knowles, & Canter, 1983) to be used for adult rather than juvenile offending (i.e., delinquency). The SRO will be used to assess the participant's involvement in delinquent acts during the past 90 days. The SRO includes a general delinquency scale as well as subscales that pertain to person offenses (e.g., assault) and property offenses (e.g., vandalism).

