be assessed with HLM, coding patients as improved or not at each time point. The main analyses will focus on during treatment effects (baseline through follow-up) but long-term effects (baseline to 3-month post-treatment follow-up) will also be analyzed (see follow-up section).

The primary outcomes are substance use is longest duration of abstinence from illicit drug use and symptoms of PTSD (NSESP-SS), continuous variables that can be transformed if needed. The primary substance use outcome is longest duration of abstinence from substances (LDA), the main outcome variable in most CM trials and the variable most strongly associated with long-term abstinence (Higgins et al., 1994, 2000, 2003; Petry et al., 2005). Linear regression will evaluate group differences in LDA, with condition as the independent variable (along with any important covariates). If data cannot be normalized, nonparametric tests will be used. While LDA is the primary substance use outcome measure, it is affected by retention as missing samples break a string of abstinence (unless preceded and followed by negative samples, and an excused 'miss' is obtained due to documented illness, court appearances, etc. usually comprising <5% of missed samples). Proportion of negative samples, in contrast, is unaffected by missing samples. Thus, we will also analyze proportion of samples negative for substances as a secondary outcome using similar analyses.

Analyses will focus on the 10-week during treatment effects, but long-term effects will also be analyzed. These will involve logistic regressions to predict substance abstinence at the 3-month follow-up, with treatment group and any important baseline characteristics (e.g., baseline sample result) included as independent variables. HLM analyses for dichotomous measures will also be conducted to evaluate substance abstinence over time between treatments from baseline throughout the 3-month follow-up. Additional secondary drug use outcomes will investigate abstinence from all substances concurrently and from each of the other drugs independently. These analyses will parallel those outlined above.

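### If a mixed-model outcome cannot be normalized, the plan replaces the score with an undefined 'improved or not', which discards information and, for the PTSD scale, may rest on a baseline with a different recall period

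*Combined protocol and SAP*

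**What the plan says.** Under Data Analysis Strategy, Aim 3, the general HLM paragraph ends with a fallback that begins "If data cannot be normalized, group by time effects will" and continues "be assessed with HLM, coding patients as improved or not at each time point". It names no test or criterion for deciding that normalization has failed. It also does not define 'improved'. The main analyses run from baseline, so the baseline row is part of the group-by-time comparison.

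The fallback covers the outcomes analysed by HLM: the weekly NSESP-SS (primary) and the secondary scales for delinquency, HIV risk, adaptive functioning and depression. For the two primary outcomes, transformation is allowed first. Longest duration of abstinence is analysed by linear regression and has its own fallback, nonparametric tests.

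The Assessments section adds three facts:
- **NSESP-SS:** "The reference period will be 'since the crime event occurred' at the screening/BL assessment and 'past month' for each subsequent assessment".
- **HRBS (HIV risk):** it "provides continuous summary scores", and "The HRBS will assess lifetime and past 3 months at baseline and the past 3 months at all other time points".
- **SRO (delinquency):** it records "involvement in delinquent acts during the past 90 days".

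Baseline adjustment is provided for in general terms: "Differences between groups that may be related to outcome will be used as covariates".

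**The concern.** Non-normality is a reason to change the test or the standard error. It is not a reason to discard the score. A two-way recode treats a small change and a large change alike, and a pilot of 20 per arm has little information to spare. With no definition written down, the threshold and reference would be chosen after the data have been seen.

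The recode also treats instruments differently. An outcome sent to it can look weaker than one kept as a score, even when the true effect is the same. The Contingency Plan compares effects across treatment areas and modifies the intervention where it appears less effective. The Specific Aims list indications of efficacy, with safety and acceptability, as conditions for moving to a powered trial. A difference created by the analysis could therefore be read as a difference in treatment effect.

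**Working it through.** The plan states no power, alpha, effect size or SD for its 40 participants, so there is no figure of its own to reproduce. Inputs from the documents: 40 randomized, 20 per arm, main analyses starting at baseline, and the recall periods quoted above. Everything else below is an assumption.

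**1. Information kept by a split (normal benchmark).** Relative efficiency = φ(z)² / [p(1 − p)], where p is the share coded improved and z is its normal quantile.
- p = 0.50: 0.3989² / 0.25 = 2/π = 0.637; × 40 = 25.5 participants.
- p = 0.80: 0.2800² / 0.16 = 0.490; × 40 = 19.6.
- p = 0.87: 0.2115² / 0.1131 = 0.396; × 40 = 15.8.

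**2. What this means at 20 per arm (illustration).** Assume one time point, normal scores, a 0.8 SD difference, two-sided alpha 0.05 and no dropout. The score gives power Φ(0.8/√(2/20) − 1.96) = Φ(0.57) = 72%. A split midway between the arms (34% v 66% improved) gives 50%. A split with 20% v 48% improved gives 47%. For 80% power the score needs 25 per arm and the midway split needs 40.

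**3. Consequences if 'improved' means change from own baseline.**
- Every baseline row is 'not improved' by construction, so it says nothing about the groups.
- A participant at zero at baseline can never be coded improved. This is possible for delinquency, because eligibility does not require recent offending. The documents give no share at zero. If it were 27% to 38% (assumed), only 40 × 0.73 = 29 down to 40 × 0.62 = 25 participants could ever be coded improved. In a score analysis the others still contribute, because a rise from zero counts.

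**4. NSESP-SS recall period.** Let the longer baseline recall raise the baseline score by d SD, with retest correlation r, and let 'improved' mean any decrease. The share coded improved with no real change is Φ(d / √[2(1 − r)]). With no shift it is 50%.

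| r | d = 0.5 | d = 1.0 |
|---|---|---|
| 0.5 | 69% | 84% |
| 0.6 | 71% | 87% |
| 0.7 | 74% | 90% |
| 0.8 | 79% | 94% |

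The documents give neither d nor r.

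**5. Does the shift damage the comparison of arms?** Assume change scores with SD 1, mean improvement 0.3 (control) and 1.1 (treated), the same shift in both arms, and 20 per arm. The share improved is Φ(mean + shift − threshold). Power is from the two-proportion normal approximation with pooled null variance.

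| Shift | Any decrease: improved, power | Decrease ≥ 0.8 SD: improved, power | Score: power |
|---|---|---|---|
| 0 | 62% v 86%, 43% | 31% v 62%, 50% | 72% |
| 0.5 | 79% v 95%, 30% | 50% v 79%, 48% | 72% |
| 1.0 | 90% v 98%, 18% | 69% v 90%, 38% | 72% |

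The shift cancels in the contrast of scores. It costs the any-decrease recode 12 points of power at 0.5 SD (from 42.5% to 30.4%). The higher-threshold recode is almost unaffected at 0.5 SD and loses power only at 1.0 SD.

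**The case against.** The strongest reply is that the fallback may never run. It needs a failed normalization, and transformation comes first for the primary outcomes. The PTSD paragraph itself specifies a continuous mixed model and mentions no recode. The 64% is a normal benchmark, applied to data that by definition would not be normal. Aim 3 is preliminary. The Overview of Design makes evidence of feasibility the condition for using the data in a grant application, and the Contingency Plan also draws on qualitative and participant input and states no significance rule. All of this stands and lowers the priority. It does not supply the missing definition, and it does not explain why abstinence duration gets nonparametric tests while the HLM outcomes get a dichotomy.

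Three stronger readings are tempting, and the documents do not support them.
- **The recall mismatch biases the PTSD comparison.** A reader might infer this, but the recall rule is the same in both arms. A common shift inflates apparent improvement over time in each arm and leaves the contrast in scores essentially unchanged.
- **The HRBS lacks a comparable baseline.** It has a lifetime and a past-3-month baseline, and every later score covers the past 3 months, so the like-for-like reference is evident. It only needs naming.
- **A definite loss of power can be attached to the weekly PTSD score or to the delinquency scale.** The documents give no distribution, share at zero, dispersion or effect size. The PTSD scale is bounded ("THE NSESP-SS is a 20-item measure including subscales"), but boundedness alone does not show that transformation would fail.

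**Conclusion.** The point holds as a limited one. The plan states a rule that replaces a score with an undefined binary outcome, although it keeps more information under the same trigger elsewhere. On a normal benchmark the recode keeps at most 64% of the information, and less when the split is uneven. For non-normal data the loss depends on a shape that the documents do not give, so the 64% is an orientation and not an estimate for this trial. The power figures above are illustrations on assumed data.

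A change-from-baseline reading adds two defects that follow from the text alone: baseline rows fixed as not improved, and an NSESP-SS reference that is not comparable with later scores. It adds a third for any instrument on which participants can start at zero. The recall mismatch harms mainly a low-threshold change recode. Priority is low to moderate.

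**What to change.** Replace the fallback sentence with:

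> If residuals remain non-normal after transformation, scores are not dichotomized. The group × time HLM is kept on the original or transformed scale, using all available data, with the p-value for the group × time term from a participant-level permutation test. For outcomes with many zeros, a rank-based analysis that keeps participants with incomplete follow-up is a sensitivity check. Improved or not is reported only descriptively after baseline, with the threshold and reference fixed per instrument before outcome data are examined. For NSESP-SS the definition uses past-month scores only; for HRBS it uses the past-3-month baseline.

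Name the check for non-normality in the same place. The rank analysis is kept as a sensitivity check because the plan chose HLM to answer the group × time question with incomplete data. If nothing else is changed, at least define 'improved' and its reference for each instrument before outcome data are examined.

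The cost is a little more programming (a permutation loop and one rank analysis) and a less simple effect measure than a proportion improved. In a simulation with assumed urn settings, permutation of a weekly slope held its size (0.051). The HLM group × time term itself was not tested, so its size should be confirmed when the test is programmed. Data collection does not change.
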